9.4.5 BASELINE DESCRIPTIVE STATISTICS

We will compare groups on baseline statistics.

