2 INTRODUCTION

2.1 STUDY RATIONALE

Despite the worldwide acknowledgment of exercise as a beneficial, non-pharmacological therapy for patients with heart failure (HF), many patients, particularly those with heart failure with preserved ejection fraction (HFpEF), do not engage in regular exercise and are unable to sustain exercise once started in a program. Patients with HFpEF report difficulties finding a routine place to exercise that includes support and accountability delivered near their home as barriers to continued exercise. These challenges are exacerbated by the ongoing COVID-19 pandemic. Therefore, we propose HEART Camp Connect that builds on the previously efficacious HEART Camp intervention. The primary objective of this study is to establish the feasibility and preliminary efficacy of the HEART Camp Connect intervention in patients with heart failure with preserved ejection fraction. We will accomplish this objective with two aims. Aim 1 examines the feasibility of administering HEART Camp Connect to patients with HFpEF. Our feasibility assessment will focus on process (e.g. recruitment rates, retention), resources (e.g. physical capacity, staff availability), management (e.g. data capture and management), and science (e.g. testing psychometrics of tools in the HFpEF population). Aim 2 tests the preliminary effects of HEART Camp Connect compared to enhanced usual care on adherence to exercise, physical activity, function, inflammation, patient-reported outcomes, and our theory-based interventional components. Impact: Exercise benefits patients with HFpEF by reducing morbidity and mortality and improving symptoms and quality of life. The proposed study uses a technology facilitated, theory-based intervention to help patients with HFpEF start and continue an exercise program over time. This feasibility, pilot study will give us data to refine the intervention and allow us to gather preliminary data for a competitive application to a federal funder.

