3 OBJECTIVES AND ENDPOINTS

OBJECTIVES	ENDPOINTS	JUSTIFICATION FOR ENDPOINTS
Primary		
Assessment of Feasibility & Acceptability	Process, resources, procedures, data management, fidelity, acceptability	Needed to refine intervention for future testing
Secondary		
Preliminary effects on exercise	Minutes of exercise/week	We are not statistically powered to test for an effect
Tertiary/Exploratory		
Preliminary effects on symptoms & interventional strategies	Symptoms, quality of life, interventional mechanisms	Evaluate symptoms and intervention strategies

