9.3 POPULATIONS FOR ANALYSES

We will not be completing inferential analyses.

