9.4 STATISTICAL ANALYSES

9.4.1 GENERAL APPROACH

We will report descriptive statistics including counts, proportions, and means only.

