9.4.3 ANALYSIS OF THE SECONDARY ENDPOINT(S)

Descriptive statistics will be calculated as appropriate.

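### Aim 2 compares coaching with enhanced usual care, but Section 9 specifies no between-arm contrast, no measure of spread or uncertainty, and no use of the Week 0 values for any outcome

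*Combined protocol and SAP*

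**What the plan says.** Section 2.1 states the comparative aim: "Aim 2 tests the preliminary effects of HEART Camp Connect compared to enhanced usual care on adherence to exercise" and on further outcomes. The same paragraph says "The primary objective of this study is to establish the feasibility and preliminary efficacy of the HEART Camp Connect intervention". Section 3 and 9.1, by contrast, give feasibility and acceptability alone as primary. Section 3 makes weekly exercise minutes the secondary endpoint and adds "We are not statistically powered to test for an effect".

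Section 9 is brief:

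- 9.1 says that there is no separate statistical plan.
- 9.3: "We will not be completing inferential analyses".
- 9.4.1: "We will report descriptive statistics including counts, proportions, and means only".
- 9.4.3, on the secondary endpoints: "Descriptive statistics will be calculated as appropriate".
- 9.4.5, on baseline: "We will compare groups on baseline statistics".
- 9.4.9 marks exploratory analyses as not applicable.

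The Schedule of Activities (1.3) collects pain, quality of life, cognition, health status and minutes of exercise at Weeks 0, 12 and 24.

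**The concern.** The randomisation exists to support a comparison between arms, and Aim 2 names that comparison. Section 9 does not say that outcomes will be summarised by arm, at which visit, or as what quantity (follow-up value, change, or difference). It names no SD and no interval, and gives the Week 0 measurements no role beyond the baseline description.

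The study is meant to supply preliminary data for a federal funding application. Readers of that application will want an effect. If the report gives means only, they will subtract one arm's mean from the other's. The result carries no statement of how uncertain it is, and at this sample size it can contain a sizeable chance difference that was already present at Week 0.

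**Working it through.** **No figure to reproduce.** Section 9.2 bases the sample size on expected recruitment. The documents give no alpha, power, effect size, SD or dropout rate, so everything below is in SD units and shows scale only.

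**Inputs from the documents**

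- Allocation 1:1 (6.3).
- Total enrolment 25 (1.1), so about 12 and 13 per arm.
- Section 6.1.1 gives n = 25 for the coached arm alone. That does not fit a total of 25 at 1:1, so both readings are computed.

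**Assumptions not in the documents**

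- Correlation r between the Week 0 and follow-up values: 0.3, 0.5 and 0.7.
- No dropout, and equal SDs in the two arms.

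**Standard error of a difference in means**

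SE = sqrt(1/n1 + 1/n2)

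- 12/13: sqrt(1/12 + 1/13) = 0.400 SD
- 25/25: sqrt(1/25 + 1/25) = 0.283 SD

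**Chance of a baseline gap of at least 0.4 SD**

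P = 2 × [1 − Φ(0.4/SE)]

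- 12/13: 0.4/0.400 = 1.00, P = 32%
- 25/25: 0.4/0.283 = 1.41, P = 16%

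**How much of such a gap reaches an unadjusted follow-up difference**

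Shift = r × gap. For a gap of 0.4 SD this is 0.12, 0.20 or 0.28 SD at r = 0.3, 0.5 or 0.7.

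**95% half-width for the between-arm difference**

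Unadjusted: t(n1+n2−2) × SE. Adjusted for the Week 0 value: t(n1+n2−3) × SE × sqrt(1 − r²). The adjusted formula ignores the small extra loss of precision caused by the baseline gap itself.

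| Reading of N | Unadjusted | r = 0.3 | r = 0.5 | r = 0.7 |
|---|---|---|---|---|
| 12/13 | 0.83 | 0.79 | 0.72 | 0.59 |
| 25/25 | 0.57 | 0.54 | 0.49 | 0.41 |

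For example, at 12/13 the unadjusted value is 2.069 × 0.400 = 0.83. At r = 0.5 the adjusted value is 2.074 × 0.400 × sqrt(0.75) = 0.72.

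The variance reduction from adjustment is r²: 9%, 25% or 49%. At r = 0.3 the gain in precision is slight. At 0.5 to 0.7 it is worth having.

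**The case against.** The strongest reply is that this is an openly descriptive pilot. The protocol disclaims power, a formal sample size calculation and inference, and a plan confined to description is a defensible choice for a feasibility study. It explains why there is no hypothesis test. It does not explain why the stated comparison has no estimate: a difference with an interval is estimation, and the interval shows the imprecision that bare means hide.

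Several stronger readings are tempting, and the documents do not support them.

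- A reader might take the baseline sentence in 9.4.5 as planned significance testing, and so call it uninformative in a randomised trial. The section is headed as descriptive, names no test, and sits under a plan that rules out inference. A descriptive baseline table is useful at about 12 per arm, because sizeable chance imbalance is common there.
- A reader might infer that the plan reports a separate summary for each arm at each visit, or that it excludes an effect estimate. Neither is written. Sections 9.4.1 and 9.4.3 mention neither arms nor visits. The contrast is unspecified, not prohibited.
- A reader might infer that the trial claims to establish efficacy as its primary objective. Section 2.1 says preliminary efficacy, and Section 3, 9.1 and 9.4.2 confine the primary endpoint to feasibility and acceptability. What remains is wording in 2.1 that does not match those sections. A power calculation would add nothing, since no one claims power.

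Two practical objections stand. The gain from adjustment depends on a correlation that the documents do not give, and it is small at 0.3. Also, Section 2.2 reports that as many as 91% of patients with heart failure do not exercise regularly, so Week 0 exercise minutes may cluster near zero. In that case the correlation may be low and a linear model may fit poorly. The fix allows for this.

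**Conclusion.** The point holds as a gap in specification. Aim 2 is comparative, and the plan as written gives it no defined contrast, no measure of uncertainty and no use of the Week 0 data. The trial can supply an estimate, but an imprecise one: about ±0.83 SD unadjusted at 12/13, or ±0.57 SD if there are 25 per arm, with adjustment narrowing this by an amount that depends on the assumed correlation. Dropout would widen every interval. The recommendation is the same under either reading of N.

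The feasibility aim is unaffected. This is an inexpensive change that should be made, and it is compatible with the protocol's position that no effect will be tested.

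**What to change.** - **9.4.3:** Report n, mean and SD by arm at Weeks 0, 12 and 24. For weekly exercise minutes, and for the other outcomes measured at Week 0, add the coached-minus-control difference at Weeks 12 and 24 adjusted for the Week 0 value, with a 95% CI and no p-value, labelled as estimation only. If Week 0 minutes cluster near zero, use a bootstrap interval or show the unadjusted difference as well.
- **9.3 and 9.4.1:** Amend to permit estimation with intervals, and add SDs to the summaries listed.
- **2.1:** In Aim 2, change *tests* to *estimates*. Align the primary objective with Section 3 and 9.1, that is, feasibility and acceptability.
- **9.4.5:** Keep the baseline table by arm and state that no significance tests will be done.
- **1.1 and 6.1.1:** Reconcile the total of 25 with the n of 25 given for the coached arm.

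No new data are needed. The cost is wording, one simple model per outcome, and intervals that will be wide.

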9.4.6 PLANNED INTERIM ANALYSES

N/A

9.4.7 SUB-GROUP ANALYSES

N/A

9.4.8 TABULATION OF INDIVIDUAL PARTICIPANT DATA

N/A

9.4.9 EXPLORATORY ANALYSES

N/A

10 SUPPORTING DOCUMENTATION AND OPERATIONAL CONSIDERATIONS

10.1 REGULATORY, ETHICAL, AND STUDY OVERSIGHT CONSIDERATIONS

10.1.1 INFORMED CONSENT PROCESS

10.1.1.1 CONSENT/ASSENT AND OTHER INFORMATIONAL DOCUMENTS PROVIDED TO PARTICIPANTS

Consent forms describing in detail the study intervention, study procedures, and risks will be given to the participant and written documentation of informed consent will be completed prior to starting the study intervention.

10.1.1.2 CONSENT PROCEDURES AND DOCUMENTATION

Consent will be documented in a private room or over the phone taking into account the participants' preferences.

10.1.2 STUDY DISCONTINUATION AND CLOSURE

This study may be temporarily suspended or prematurely terminated if there is sufficient reasonable cause. Written notification, documenting the reason for study suspension or termination, will be provided

by the suspending or terminating party to <study participants, investigator, funding agency, and regulatory authorities>. If the study is prematurely terminated or suspended, the Principal Investigator (PI) will promptly inform study participants, the Institutional Review Board (IRB), and sponsor/funding agency and will provide the reason(s) for the termination or suspension. Study participants will be contacted, as applicable, and be informed of changes to study visit schedule.

Circumstances that may warrant termination or suspension include, but are not limited to:

- Determination of unexpected, significant, or unacceptable risk to participants
- Demonstration of efficacy that would warrant stopping
- Insufficient compliance of study staff to the protocol (ie, significant protocol violations)
- Data that are not sufficiently complete and/or evaluable
- Determination that the primary endpoint has been met
- Determination of futility

The study may resume once concerns about safety, protocol compliance, and data quality are addressed, and satisfy the funding agency, sponsor, IRB, Food and Drug Administration (FDA), or other relevant regulatory or oversight bodies (OHRP, DSMB).]

10.1.3 CONFIDENTIALITY AND PRIVACY

Participant confidentiality and privacy is strictly held in trust by the participating investigators, their staff, the safety and oversight monitor(s), and the sponsor(s) and funding agency. This confidentiality is extended to the data being collected as part of this study. Data that could be used to identify a specific study participant will be held in strict confidence within the research team. No personally-identifiable information from the study will be released to any unauthorized third party without prior written approval of the sponsor/funding agency.

All research activities will be conducted in as private a setting as possible.

The study monitor, other authorized representatives of the sponsor or funding agency, representatives of the Institutional Review Board (IRB), regulatory agencies or representatives from companies or organizations supplying the product, may inspect all documents and records required to be maintained by the investigator, including but not limited to, medical records (office, clinic, or hospital) and pharmacy records for the participants in this study. The clinical study site will permit access to such records.

The study participant's contact information will be securely stored at each clinical site for internal use during the study. At the end of the study, all records will continue to be kept in a secure location for as long a period as dictated by the reviewing IRB, Institutional policies, or sponsor/funding agency requirements.

Measures Taken to Ensure Confidentiality of Data Shared per the NIH Data Sharing Policies

It is NIH policy that the results and accomplishments of the activities that it funds should be made available to the public (see <https://grants.nih.gov/policy/sharing.htm>). The PI will ensure all mechanisms used to

share data will include proper plans and safeguards for the protection of privacy, confidentiality, and security for data dissemination and reuse (e.g., all data will be thoroughly de-identified and will not be traceable to a specific study participant). Plans for archiving and long-term preservation of the data will be implemented, as appropriate.

Certificate of Confidentiality

To further protect the privacy of study participants, the Secretary, Health and Human Services (HHS), has issued a Certificate of Confidentiality (CoC) to all researchers engaged in biomedical, behavioral, clinical or other human subjects research funded wholly or in part by the federal government. Recipients of NIH funding for human subjects research are required to protect identifiable research information from forced disclosure per the terms of the NIH Policy (see <https://humansubjects.nih.gov/coc/index>). As set forth in 45 CFR Part 75.303(a) and NIHGPS Chapter 8.3, recipients conducting NIH-supported research covered by this Policy are required to establish and maintain effective internal controls (e.g., policies and procedures) that provide reasonable assurance that the award is managed in compliance with Federal statutes, regulations, and the terms and conditions of award. It is the NIH policy that investigators and others who have access to research records will not disclose identifying information except when the participant consents or in certain instances when federal, state, or local law or regulation requires disclosure. NIH expects investigators to inform research participants of the protections and the limits to protections provided by a Certificate issued by this Policy.

10.1.4 FUTURE USE OF STORED SPECIMENS AND DATA

Data collected for this study will be analyzed and stored at REDCap. After the study is completed, the de-identified, archived data will be transmitted to and stored at the University of Nebraska, for use by other researchers including those outside of the study.

10.1.6 SAFETY OVERSIGHT

Safety oversight will be under the direction of a Data and Safety Monitoring Board (DSMB)/Safety Monitoring Committee (SMC) composed of individuals with the appropriate expertise.

10.1.7 CLINICAL MONITORING

Clinical site monitoring will be conducted to ensure that the rights and well-being of trial participants are protected, that the reported trial data are accurate, complete, and verifiable, and that the conduct of the trial is in compliance with the currently approved protocol/amendment(s), with International Council on Harmonisation Good Clinical Practice (ICH GCP), and with applicable regulatory requirement(s).

10.1.8 QUALITY ASSURANCE AND QUALITY CONTROL

This is single site study

10.1.9 DATA HANDLING AND RECORD KEEPING

10.1.9.1 DATA COLLECTION AND MANAGEMENT RESPONSIBILITIES

Data collection will be the responsibility of the clinical trial staff at the site under the supervision of the site investigator. The investigator will be responsible for ensuring the accuracy, completeness, legibility, and timeliness of the data reported.

All source documents will be completed in a neat, legible manner to ensure accurate interpretation of data.

Hardcopies of the study visit worksheets will be provided for use as source document worksheets for recording data for each participant consented/enrolled in the study. Data recorded in the electronic case report form (eCRF) derived from source documents will be consistent with the data recorded on the source documents.

Data will be collected and managed in REDCap.

10.1.9.2 STUDY RECORDS RETENTION

Study documents will be retained for a minimum of 2 years after the last approval of a marketing application in an International Council on Harmonisation (ICH) region and until there are no pending or contemplated marketing applications in an ICH region or until at least 2 years have elapsed since the

formal discontinuation of clinical development of the study intervention. These documents should be retained for a longer period, however, if required by local regulations. No records will be destroyed without the written consent of the sponsor/funding agency, if applicable. It is the responsibility of the sponsor/funding agency to inform the investigator when these documents no longer need to be retained.]

10.1.10 PROTOCOL DEVIATIONS

This protocol defines a protocol deviation as any noncompliance with the clinical trial protocol, International Council on Harmonisation Good Clinical Practice (ICH GCP), or Manual of Procedures (MOP) requirements. The noncompliance may be either on the part of the participant, the investigator, or the study site staff. As a result of deviations, corrective actions will be developed by the site and implemented promptly.

These practices are consistent with ICH GCP:

- Section 4.5 Compliance with Protocol, subsections 4.5.1, 4.5.2, and 4.5.3
- Section 5.1 Quality Assurance and Quality Control, subsection 5.1.1
- Section 5.20 Noncompliance, subsections 5.20.1, and 5.20.2.

It will be the responsibility of the site investigator to use continuous vigilance to identify and report deviations within <specify number> working days of identification of the protocol deviation, or within <specify number> working days of the scheduled protocol-required activity. All deviations will be addressed in study source documents, reported to <specify NIH Institute or Center (IC)> Program Official and <specify Data Coordinating Center or sponsor>. Protocol deviations will be sent to the reviewing Institutional Review Board (IRB) per their policies. The site investigator will be responsible for knowing and adhering to the reviewing IRB requirements. Further details about the handling of protocol deviations will be included in the MOP.

10.1.11 PUBLICATION AND DATA SHARING POLICY

This study will be conducted in accordance with the following publication and data sharing policies and regulations:

National Institutes of Health (NIH) Public Access Policy, which ensures that the public has access to the published results of NIH funded research. It requires scientists to submit final peer-reviewed journal manuscripts that arise from NIH funds to the digital archive PubMed Central upon acceptance for publication.

This study will comply with the NIH Data Sharing Policy and Policy on the Dissemination of NIH-Funded Clinical Trial Information and the Clinical Trials Registration and Results Information Submission rule. As such, this trial will be registered at ClinicalTrials.gov, and results information from this trial will be submitted to ClinicalTrials.gov. In addition, every attempt will be made to publish results in peer-reviewed journals. Data from this study may be requested from other researchers x years after the completion of

the primary endpoint by contacting <specify person or awardee institution, or name of data repository>. Considerations for ensuring confidentiality of these shared data are described in Section 10.1.3.

10.1.12 CONFLICT OF INTEREST POLICY

The independence of this study from any actual or perceived influence, such as by the pharmaceutical industry, is critical. Therefore, any actual conflict of interest of persons who have a role in the design, conduct, analysis, publication, or any aspect of this trial will be disclosed and managed. Furthermore, persons who have a perceived conflict of interest will be required to have such conflicts managed in a way that is appropriate to their participation in the design and conduct of this trial. The study leadership in conjunction with the Great Plains IDeA CTR has established policies and procedures for all study group members to disclose all conflicts of interest and will establish a mechanism for the management of all reported dualities of interest.

10.2 ADDITIONAL CONSIDERATIONS

N/A

10.3 ABBREVIATIONS AND SPECIAL TERMS

AE	Adverse Event
CFR	Code of Federal Regulations
CLIA	Clinical Laboratory Improvement Amendments
CMP	Clinical Monitoring Plan
COC	Certificate of Confidentiality
CONSORT	Consolidated Standards of Reporting Trials
CRF	Case Report Form
DCC	Data Coordinating Center
DHHS	Department of Health and Human Services
DSMB	Data Safety Monitoring Board
DRE	Disease-Related Event
EC	Ethics Committee
eCRF	Electronic Case Report Forms
FDA	Food and Drug Administration
FDAAA	Food and Drug Administration Amendments Act of 2007
FFR	Federal Financial Report
GCP	Good Clinical Practice
GLP	Good Laboratory Practices
GMP	Good Manufacturing Practices
GWAS	Genome-Wide Association Studies
HF	Heart Failure
HFpEF	Heart Failure with Preserved Ejection Fraction
HIPAA	Health Insurance Portability and Accountability Act
IB	Investigator's Brochure
ICH	International Council on Harmonisation
ICMJE	International Committee of Medical Journal Editors
IDE	Investigational Device Exemption

IND	Investigational New Drug Application
IRB	Institutional Review Board
ISM	Independent Safety Monitor
ITT	Intention-To-Treat
LSMEANS	Least-squares Means
MedDRA	Medical Dictionary for Regulatory Activities
MOP	Manual of Procedures
NCT	National Clinical Trial
NIH	National Institutes of Health
NIH IC	NIH Institute or Center
OHRP	Office for Human Research Protections
PI	Principal Investigator
QA	Quality Assurance
QC	Quality Control
SAE	Serious Adverse Event
SAP	Statistical Analysis Plan
SMC	Safety Monitoring Committee
SOA	Schedule of Activities
SOC	System Organ Class
SOP	Standard Operating Procedure
UP	Unanticipated Problem
US	United States

